7.2 Planned Analyses

In this mixed methods study, we will perform concurrent qualitative and quantitative data collection and subsequent merged analysis. We will analyze quantitative data in Stata,²⁹ with statistical support from a biostatistician. Qualitative responses will be transcribed and coded by members of the research teams using NVivo®. We will identify emerging themes using the constant comparative method. A repeated measures linear mixed model approach will be used for analysis. The primary analyses will compare changes in COVID-19 knowledge and of emotional competence before and after participation between the intervention and wait-list control groups. Similar analyses will be measured for secondary outcomes.

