Implementing and Evaluating a Wellness and Social-Emotional Learning Program for Refugee Children During the COVID-19 Pandemic: EMPOWER

(Emotions Program Outside the Clinic and Wellness Education for Refugees)

Protocol Number

2000030455

ClinicalTrials.gov Identifier: NCT04931888

Protocol and Statistical Analysis Plan

February 20, 2022

Version #3

Synopsis

Purpose

Our overall goal is to pilot an adaptation of an established Social-Emotional Learning (SEL) Program with novel wellness and COVID-19 safety components that are trauma-informed and culturally-specific in a resettled refugee community.

Objectives

In this pilot, “EMPOWER” (Emotions Program Outside the clinic and Wellness Education for Refugees), we aim:

1. To assess implementation outcomes (adoption, acceptability, and feasibility) of EMPOWER with refugee children and families during the COVID-19 pandemic through longitudinal evaluations and measurements of feasibility, acceptability, and attrition.
2. To evaluate the impact of EMPOWER by assessing (a) children’s SEL competence and (b) children’s and family’s COVID-19 knowledge.

Study Population

The study population will include families who are connected with Elena’s Light, a trusted community non-profit organization that supports refugee families in the New Haven region.

Because the model of adaptation and delivery will be culturally specific for Afghan refugees (the majority of recent refugees in the New Haven area are from Afghanistan), eligible participants will include Afghan refugee children, 5-15 years old, who have completed ≥ 1 year of school in US. One parent/guardian will also be surveyed in the pre- and post-evaluation on Zoom.

Number of Participants

A total of approximately 75 children from 30 family units will be recruited to participate, along with at least one parent/guardian from each family. This will include 50 children from 20 family units in the intervention group and 25 children from 10 family units in the control group.

Study Design

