EMPOWER is an adapted SEL and wellness education initiative delivered to a community of refugee families that was developed through a pre-pilot in the New Haven Afghan refugee community in 2020. Unlike traditional school-based SEL curricula, EMPOWER partners with community organizations to provide translated and trauma-informed wellness education to family units. The program combines in-person (socially distant) and remote delivery of culturally-informed physical, emotional, and medical wellness tools adapted from evidenced-based behavioral medicine, refugee trauma and recovery, and community health research. Over two weeks, enrollees participate in six in-person sessions (two hours each). They also complete eight, one-hour, weekly Zoom sessions during and beyond the in-person curriculum. At-home Zoom technical support is provided as needed. Each family unit is guided through in-person and online components by a facilitator. The EMPOWER curriculum focuses on the core competency of self-awareness, a core element of emotional competence, from the Collaboration for Academic Social and Emotional Learning (CASEL) framework. Facilitators include interns, health-providers, and community partners. We have published a detailed EMPOWER manual, which we will iteratively modify, through an online request portal.

Intervention:

We will use implementation science methods and apply an Intervention Mapping framework to refine and assess the adoption, acceptability, and feasibility of EMPOWER. The program will include virtual and in-person SEL, COVID-19 safety, and physical activity instructions. Program administrators will also respond to and track disclosure of and/or identification of mental health, medical, or other needs.

Data Collection and Measures:

We will conduct a mixed methods evaluation—using concurrent qualitative and quantitative data collection and merged analysis—to survey parents and their children (over Zoom) at early and late time-points of their involvement in the program. Interview guides and survey

tools will be developed with community partners and will be based upon previously-studied measures used for war-affected families. In addition to demographic covariates (age, gender, languages, years in the US), we will collect data and assess implementation outcomes as well as primary and secondary outcome measures. Questions will be asked to parents about each child and to the children directly.

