5.2 Number of Participants

We will recruit a total of 75 children from a total of approximately 30 family units.

After recruitment, we will assign participants to an intervention group (50 children from 20 family units) and a wait-list control group (25 children from 10 family units) and will stagger administration of the EMPOWER curriculum to the two groups.

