5.3 Eligibility Criteria

Eligibility will be determined in partnership with our community partner, Elena's Light, with approval by the PI based upon eligibility status.

- Because we are recruiting by family unit, we will allow a wide age range of children, from 5-15 years old.
- The model of adaptation and delivery will be culturally specific for Afghan refugees (the majority of recent refugees in the New Haven area are from Afghanistan).
- Thus, eligible participants will include:
 - Afghan refugee children
 - 5-15 years old
 - Who have completed ≥ 1 year of school in US.
 - Who are able to safely attend outdoor sessions with one parent/guardian

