6.2 Method of Assignment/Randomization (if applicable)

Not applicable. Intervention and control group designations will be based upon geographic location to easily access the outdoor location of the EMPOWER program.

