7.7 Handling of Missing Data

A biostatistical consultant will be part of the research team who can help to determine how to handle missing data, depending on quantity of missing data. We will consider dropping certain individual responses and/or imputation methodology depending on how much data is missing.

8 Data/Specimen Handling and Record Keeping

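### The mixed model in Section 7.2 requires no family-level term although children are recruited by family; if siblings' changes correlate and only repeated measures within child are modelled, the standard error of the group difference in change is too small.

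*Combined protocol and SAP*

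**What the plan says.** Section 7.2, and the Analysis Plan paragraph of Section 4 in the same words, describe the quantitative model in one sentence: "A repeated measures linear mixed model approach will be used for analysis". The primary comparison is the change in COVID-19 knowledge and in emotional competence between the intervention and wait-list groups. Section 7.2.1 adds nothing to this. Nowhere do the documents mention a family random effect, a family-by-time term, cluster-robust variance, an intraclass correlation or a design effect.

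The design is built on families:

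- Section 5.3 (recruitment): "Because we are recruiting by family unit, we will allow a wide age range of children, from 5-15 years old".
- Section 5.2 (numbers): 50 children from 20 families in the intervention group, 25 children from 10 families in the control group.
- Section 6.2 (assignment): "Intervention and control group designations will be based upon geographic location to easily access the outdoor location of the EMPOWER program". Children of one household therefore share a group.
- Sections 4 and 6.1 (delivery): "Each family unit is guided through in-person and online components by a facilitator".
- Sections 4 and 6.1 (measurement): "Questions will be asked to parents about each child and to the children directly".

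On missing data, Section 7.7 says only: "We will consider dropping certain individual responses and/or imputation methodology depending on how much data is missing".

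**The concern.** Exposure does not vary within a family. If siblings' changes are positively correlated, 75 children carry less information about the group difference than 75 independent children would. The only dependence that Section 7.2 names is the repeated measurement. An analyst who follows it literally would model two scores within each child and treat siblings as independent.

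Two features make a positive correlation of change plausible. Delivery is organised by family, and one parent may rate several siblings. Confidence intervals for the group difference would then be too narrow and p-values too small. The plan sets no alpha and no progression rule, so no documented decision is at risk. What is at risk is the reported precision of the preliminary efficacy result, which the plan means to carry into larger trials.

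**Working it through.** **Inputs from the documents.** Section 7.1 derives the sample from session capacity: 10 children x 5 sessions = 50 and 4 families x 5 sessions = 20. Adding the controls gives 50 + 25 = 75 children and 20 + 10 = 30 families. These figures reproduce exactly. Mean family size is 50/20 = 25/10 = 2.5 in each group.

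**Assumptions not in the documents.** Two-sided 5% test; within-family intraclass correlation (ICC) of the change score from 0.05 to 0.5; family sizes either 2-3 (half each) or 1-4; either complete data or 20% of post scores missing at random.

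**Step 1: which correlation matters.** The target is a difference in change. A stable family level enters pre and post scores alike and cancels from change, exactly so with complete pairs. Only a family effect that differs between the two time points matters, so the relevant quantity is the ICC of change.

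**Step 2: design effect, correlation in both arms.** The variance is multiplied by D = 1 + (m* - 1) x ICC, where m* is the sum of squared family sizes divided by the sum of family sizes.

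- Sizes 2-3: m* = (4 + 9)/(2 + 3) = 2.6, so D = 1 + 1.6 x ICC.
- Sizes 1-4: m* is about 3, so D is about 1 + 2 x ICC.

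The child-only standard error is too small by 1 - 1/sqrt(D). The actual type I error is 2 x [1 - Phi(1.96/sqrt(D))].

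**Step 3: correlation in the intervention arm only.** Controls are evaluated before they receive the curriculum (schedule in Section 6.1) and have only written materials until then (Section 5.1). In units of the variance of change, the difference has variance 1/50 + 1/25 = 0.02 + 0.04 = 0.06. The intervention arm supplies 0.02/0.06 = one third of this, so the multiplier falls to 1 + (m* - 1) x ICC/3.

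| ICC of change | D, both arms | SE too small by | Type I, both arms | Type I, intervention arm only |
|---|---|---|---|---|
| 0.05 | 1.08-1.10 | 4-5% | 5.9-6.2% | 5.3-5.4% |
| 0.1 | 1.16-1.20 | 7-9% | 6.9-7.4% | 5.6-5.8% |
| 0.3 | 1.48-1.60 | 18-21% | 10.7-12.1% | 6.9-7.4% |
| 0.5 | 1.80-2.00 | 25-29% | 14.4-16.6% | 8.2-9.0% |

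Example at ICC 0.3, sizes 2-3: D = 1 + 1.6 x 0.3 = 1.48 and sqrt(D) = 1.217. The standard error is short by 1 - 1/1.217 = 17.8%, and type I error is 2 x [1 - Phi(1.96/1.217)] = 10.7%.

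**Step 4: simulation.** The settings were 20 against 10 families and no true effect, with 4,000 runs per setting for REML mixed models and 20,000 for child-level tests on change.

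- Child as the only clustering level, both arms: 6.7-8.0% at ICC 0.1, 10.7-11.9% at 0.3 and 13.6-16.3% at 0.5. Further simulations ran from 9.7% to 12.0% at 0.3 and up to 17.0% at 0.5.
- Child only, correlation in the intervention arm only: 5.6-6.1%, 6.5-7.3% and 8.0-9.4% at the same three ICCs.
- Child only, ICC 0.05, mixed model with 20% missing: 5.4% and 5.8%, against 5.5% and 5.4% at ICC 0. These are indistinguishable within simulation error.
- Family intercept added but no family-by-time term, ICC 0.3 in both arms: 10.7-11.8%, so no repair.
- Family, family-by-time and child terms with Kenward-Roger: 4.0-5.8% in all both-arm settings, 3.6-4.4% when only the intervention arm is correlated.
- Reported against actual standard error, child-only model, complete data, ICC 0.3: 0.244 against 0.299 (sizes 2-3) and 0.243 against 0.309 (sizes 1-4). The full model reports 0.297 and 0.300.

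**The case against.** The strongest reply is that Section 7.2 names a class of model, not a faulty model. A linear mixed model can carry a family level, and a biostatistician is on the team. That stands. A reader might infer that the plan analyses siblings as independent; the documents do not say so. The defect is that the text requires no family term, and that the obvious repair, a family intercept, would not work.

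A reader might also infer that the documents establish correlated change among siblings. They do not.

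- The facilitator sentence does not say that each family has its own facilitator. One who serves several families would create clustering above the family. Delivery by facilitator also mainly supports correlation in the intervention arm, where the inflation is much smaller.
- A parent's stable rating tendency cancels from change. Only a shift over time would matter, and it would not touch children's self-reports.

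Parents' own scores might seem to be affected too, because the Synopsis speaks of families joining "along with at least one parent/guardian from each family". That phrase concerns who takes part. The Synopsis sentence on evaluation refers to one parent or guardian being surveyed, and with one per family there is nothing to cluster.

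Finally, the near-nominal error rate of the proposed model assumes no session-group or location effect. In a simulation with family ICC 0.2 and an assumed session-group ICC of 0.05 or 0.10 in both arms (five intervention and three assumed control groups), a comparison of family means rejected in 7.8% and 10.3% of runs. With effects in the intervention arm only, it rejected in 5.0% and 6.0%. This limits what the fix achieves, but it is no reason to leave family out.

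**Conclusion.** The point holds as a conditional one and should be fixed. If repeated measures within child are the only dependence modelled and siblings' changes correlate, the standard error of the group difference in change is too small. At an assumed ICC of change of 0.1 / 0.3 / 0.5, nominal 5% type I error becomes roughly 7-8 / 10-12 / 13-17% with correlation in both arms, and roughly 5-6 / 6.5-7 / 8-10% with correlation in the intervention arm only. At 0.05 the effect is negligible.

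Every ICC, the family-size patterns, the 5% level and the missing-data rate are assumptions. The point covers outcomes with more than one record per family: children's self-reports and parent reports about each child. It does not show that any planned decision would be wrong, since the plan states no threshold. Confidence is medium, because the sibling correlation is plausible but undocumented.

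**What to change.** In Section 7.2, and in the matching paragraph of Section 4, state the following for every primary and secondary outcome with more than one record per family:

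- Fixed effects: group, time and group-by-time.
- Random effects: family, family-by-time (a separate family deviation at each time point) and child within family.
- Fitting: REML on all available pre and post scores, with a small-sample degrees-of-freedom correction such as Kenward-Roger, given about 30 families.
- Fallback if the model does not converge: a change-score model with a family random intercept, or a comparison of family-mean changes (20 against 10 families). These match the mixed model only with complete pairs and drop children without a post score. They should therefore not come first while Section 7.7 leaves the handling of missing data open.

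State also that one parent per family is surveyed, if that is the intention.

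The cost is two or three sentences and a family identifier in the analysis file, with no new data. There are three downsides. Standard errors are about 18-25% larger at ICC 0.3 (0.297/0.244 = 1.22 and 0.300/0.243 = 1.23 in the complete-data simulations). The test is slightly conservative if sibling correlation is absent (4.1-4.3%) or confined to the intervention arm (3.6-4.4%). The added variance component may be estimated at zero.

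The change restores the nominal error rate only if there is no further clustering by session group or location. It does nothing about confounding from assignment by location.

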7.2.1 Secondary Objective Analyses (if applicable)

See above.

7.2.2 Analysis of Subject Characteristics (if applicable)

Descriptive demographic characteristics will include: age, gender, languages, years in the US.

7.2.3 Interim Analysis (if applicable)

N/A

7.3 Data Relevance

The data collected will specifically answer the research question of: can an adaptation of an established Social-Emotional Learning (SEL) curriculum effectively improve Social-Emotional wellness for refugee children and their families? By evaluating emotional competence and exploring secondary outcomes related to mental and behavioral health, we will be able to understand the impact of EMPOWER on refugee children's health.

7.4 Data Coding

We will use the constant comparative method to analyze themes in the qualitative data and iteratively refined the interview guide over the course of the interviews.³⁰ A two-person coding team will analyze written transcripts using grounded theory methodology.³⁰

Discrepancies will be resolved by discussion, and the research team will then review codes and emerging themes and agreed upon trends and themes from qualitative responses. The mixed-method results will be integrated with merged analysis which compared and contrasted divergences.²⁵

7.5 Data Analysis Tools

Both Dedoose and Stata will be used in analysis.

7.6 Data Monitoring

Data will be kept on a password protected computer of the PI and/or in Yale's secure Box location.

7.7 Handling of Missing Data

A biostatistical consultant will be part of the research team who can help to determine how to handle missing data, depending on quantity of missing data. We will consider dropping certain individual responses and/or imputation methodology depending on how much data is missing.

8 Data/Specimen Handling and Record Keeping

8.1 Subject Data Confidentiality

Participant confidentiality and privacy is strictly held in confidence by the participating investigators, their staff, and the sponsor(s)/funding agency. Therefore, the study protocol, documentation, data, and all other information generated will be held in strict confidence.

All research activities will be conducted in as private a setting as possible.

Representatives of the Institutional Review Board (IRB), regulatory agencies or study sponsor/funding agency may inspect all documents and records required to be maintained by the investigator for the participants in this study. The study site will permit access to such records.

The study participant's contact information will be securely stored at each study site for internal use during the study. At the end of the study, all records will continue to be kept in a secure location for as long a period as dictated by the reviewing IRB, Institutional policies, regulatory, or sponsor/funding agency requirements.

Study participant research data, which is for purposes of statistical analysis and scientific reporting, will be transmitted to and stored on password-protected Yale Box server. This will not include the participant's contact or identifying information. Rather, individual participants and their research data will be identified by a unique study identification number. The study data entry and study management systems used will be secured and password protected. At the end of the study, all study databases will be de-identified and archived at the password protected computer of the PI.

Taping of Zoom conversations will be recorded, with permission. Transcriptions and audio files will not include participant's demographic data and will also be kept on password protected Yale Box and Dedoose files.

8.2 Data Quality Assurance

In order to maintain quality control, all researchers will follow and update the EMPOWER manual, available via request through an online server.²⁴ Training of research assistants will include observed data collection sessions.

8.3 Data or Specimen Storage/Security

As noted above, data will be deidentified with participant IDs, which will be indexed on the PI's password protected computer. Deidentified data, which will include responses to validated instruments, transcripts and audio recordings without demographic data, will be stored on password-protected Yale Box.

8.4 Study Records

The PI will be responsible for maintaining study records on a password protected computer. These records will include:

- Documentation of informed consent

- COVID symptom screening records (administered for in-person classes) and attendance records (for Zoom and in-person classes)
- Participant identifier ID index

Additional records will be kept on Yale secured box:

- Audio recordings and transcripts without participant demographic data
- Responses to all validated survey tools

8.5 Access to Source

Source documents (all electronic word documents) will include all data collection materials completed over Zoom with families. Qualitative and quantitative responses will be compiled into Dedoose and Stata for analysis, respectively. Deidentified documents will be available in Yale Box, shared with co-investigators. Identifiable data will be kept on the PI's password protected computer.

8.6 Retention of Records

Records will be kept for at least 3 years on the PI's password protected computer and indefinitely, or until the PI chooses to destroy it, in Yale Box.

8.7 Data and Safety Monitoring Plan

We do not anticipate any adverse events. The principal investigator (PI) will monitor the data, assure protocol compliance, and conduct the safety reviews at least annually. The PI evaluate whether the study should continue unchanged, require modifications, or close to enrollment. Any Reportable Events (which are events that are serious or life-threatening and unanticipated (or anticipated but occurring with a greater frequency than expected) and possibly, probably, or definitely related) Unanticipated Problems Involving Risks to Subjects or Others will be reported to the IRB and any appropriate funding and regulatory agencies. Unanticipated Problems Involving Risks to Subjects or Others that may require a temporary or permanent interruption of study activities (if possible) will be reported, followed by a written report within 5 calendar days of my becoming aware of the event to the IRB and any appropriate funding and regulatory agencies. The PI will apprise fellow investigators and study personnel of all UPIRSOs and adverse events that occur during the conduct of this research project. The PI will report all UPIRSOs and adverse events that occur during the conduct of this research project to other applicable oversight bodies as required within applicable reporting timeframes.

9 Study Considerations

